## 5. STUDY DESIGN

A prospective single-centre pilot study will be conducted to investigate this topic. Fifteen patients with both ischemic and non-ischemic cardiomyopathy resulting in left ventricular myocardial scar and elected to CRT implant at the OUH, will be enrolled in this study.

Compared to standard practice, additional research investigations will be a baseline visit for eligibility assessment, informed consent and pre-CRT implant cardiac MRI, a three-dimensional electroanatomical map reconstruction of the CS venous system during the standard CRT implant and the evaluation of the acute haemodynamic response (AHR, percentage increase of LV-dP/dT max) of MPP over conventional single-site LV pacing during the CRT implant.

1. The cardiac Magnetic Resonance Imaging (MRI) will be performed in each patient 1-2 weeks before the CRT implant during the baseline visit. It will provide information regarding left ventricular (LV) function and volumes, characterization of LV tissue, presence and location of myocardial scar, anatomy of the CS venous system. Moreover, the peri-scar region (viable tissue immediately close to the scar) and the remote

|  |                                    |                                      |
|--|------------------------------------|--------------------------------------|
| Subject: Research protocol                    | Short Title: SCAR MPP study | Chief Investigator: [name] |
| Version/Date: 1.1 /6 th April 2019 | IRAS Ref: 211326            | Ethics Ref: 16/SC/0662        |

myocardium (viable tissue farther from it) will be identified according to a 17-segments LV segmentation model (see intervention section for more details).

2. A de-novo CRT implant will be performed under fluoroscopic guidance as per standard care. All subjects will be implanted with a regulatory approved St. Jude Medical CRT device compatible with MPP feature (models n° CD3271-40(Q), CD3371-40(Q), CD3371-40C(QC) or newer) and St. Jude Medical quadripolar left ventricular lead (Quartet 1458Q or newer). The choice of the right ventricular and right atrial leads will be left to the operator. After implant of the right ventricular and right atrial leads, a CS venogram will be then performed as per standard practice (see intervention section for more details).

3. A three-dimensional electroanatomical map of the CS venous system will be constructed with Precision mapping system and a Biotronik Vision wire (Biotronik Se & Co. KG, Berlin, Germany) by using the CS venogram as a guide. The map will be merged with the correspondent cardiac MRI images in order to locate the myocardial scar in respect to the CS branches. This will allow the identification of two target CS branches for the study measurements, one located in the peri-scar region and one located in the remote myocardium.

4. A Certus PressureWire will be then introduced into the LV. A PhysioMon software (Radi Medical Systems, Uppsala, Sweden) will be used for electronic calculation of the LV-dP/dTmax from every heartbeat for a period of at least thirty seconds to ensure steady-state conditions. The baseline LV-dP/dTmax will be measured during ventricular spontaneous rhythm.

A St. Jude Medical quadripolar left ventricular lead will be sequentially placed in the “peri-scar” CS branch and in the “remote myocardium” CS branch. In each site the percentage increase in LV-dP/dTmax (Acute Haemodynamic Response, AHR) produced by both conventional single-site and MPP LV pacing to will be measured. All 4 poles of the quadripolar lead will be used in turn for conventional single-site LV pacing, 3 different configurations will be used in turn for MPP. The LV-dP/dTmax will be recorded for each pacing configuration in order to identify the MPP and the single-site LV pacing configurations producing the best AHR (best percentage increase of LV-dP/dTmax).

The AHR produced by the best MPP configuration in peri-scar region will be compared with the AHR produced by the best MPP configuration in the remote myocardium. Moreover, the percentage increase of LV-dP/dTmax produced by the best MPP configuration over the best conventional single-site LV pacing in the peri-scar region will be compared with the same measurement obtained in the remote myocardium.

The decision about the final position of the LV lead and the activation of MPP feature after the CRT implant will be left to operator preference. This is usually decided on the basis of minimum pacing output required to achieve capture, lead stability and ECG changes suggestive of good resynchronization.

As standard practice, the patient will be discharged the day after the procedure. A pre-discharge review will be performed by the patient's standard care team. Any recorded peri-procedural complications will be communicated to the research team who will report them in the correspondent study CRF.

|  |                                    |                                      |
|--|------------------------------------|--------------------------------------|
| Subject: Research protocol                    | Short Title: SCAR MPP study | Chief Investigator: [name] |
| Version/Date: 1.1 /6 th April 2019 | IRAS Ref: 211326            | Ethics Ref: 16/SC/0662        |
| Page 10 of 27                                 |                                    |                                      |

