- the research CRT implant will take longer than a standard procedure (we estimate 20-30 additional minutes on average) due to movement of the left ventricular lead from one vein to another and due to AHR measurements;
- there will be a slightly increased risk of damage to the CS venous system from extra manipulation of leads within it.

Specific S Jude Medical devices and quadripolar leads allowing MPP algorithm will be chosen. They are already used as part of standard care at the OUH and they are CE-marked. The MPP feature will be used only for a few minutes during the implant procedure, therefore it will have a negligible effect on battery duration. The decision to use MPP after the implant will be left to the operator.

The potential risks and benefits of both procedures and implants will be explained to participants as part of their standard care.

|  |                                    |                                      |
|--|------------------------------------|--------------------------------------|
| Subject: Research protocol                    | Short Title: SCAR MPP study | Chief Investigator: [name] |
| Version/Date: 1.1 /6 th April 2019 | IRAS Ref: 211326            | Ethics Ref: 16/SC/0662        |

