The  $LV-dP/dT_{max}$  will be measured during spontaneous ventricular rhythm. A St. Jude Medical quadripolar left ventricular lead (Quartet 1458Q or newer) will be then sequentially placed in the “peri-scar” CS branch and in the “remote myocardium” CS branch and the  $LV-dP/dT_{max}$  will be measured during conventional single-site and MPP LV pacing in each site. In each site the AHR to both conventional single-site and MPP LV pacing will be performed by measuring the percentage change in  $LV-dP/dT_{max}$  compared to spontaneous ventricular rhythm. Different single-site (all 4 poles in turn) and MPP (3 configurations) LV pacing settings will be tested to this aim in order to identify the best MPP and single-site LV pacing configurations.

The AHR produced by the best MPP configuration in peri-scar region will be compared with the AHR produced by the best MPP configuration in the remote myocardium. Moreover, the percentage increase of  $LV-dP/dT_{max}$  produced by the best MPP configuration over the best conventional single-site LV pacing in the peri-scar region will be compared with the same measurement obtained in the remote myocardium.

All measurements will be repeated at least twice in order to make sure they are reliable and reproducible. The pressure wire and the sheath will be removed after all measurements are complete.

Data will be electronically captured from the pressure wire and automatically extracted on an excel database.

The  $LV-dP/dT_{max}$  measurements will not influence the operator’s decision about the final position of the LV lead. This will be dictated, as standard practice, by minimum pacing output required to achieve capture, lead stability and ECG changes suggestive of good resynchronization.

All subjects will be implanted with a regulatory approved St. Jude Medical CRT device compatible with MPP feature (models n° CD3271-40(Q), CD3371-40(Q), CD3371-40C(QC) or newer).

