**STATISTICS AND ANALYSIS**

### **12.1. The Number of Participants**

This is a pilot study that aims at investigating a possible relation between scar location and AHR to MPP more than proving a statistical significant different between AHR to MPP in the peri-scar region compared to the remote myocardium. Therefore, a small sample size of 15 patients has been chosen just in order to confirm the validity of the study hypothesis to be further investigated in a bigger study.

Of note, a recent study (13) has documented a variable AHR to MPP over single-site LV pacing with a percentage increase in LV-dP/dT between 0% and 40% according to LV site. If our hypothesis is confirmed and the best and worst MPP sites correspond to peri-scar and remote-myocardium respectively, 15 patients could be also enough in order to show a statistically significant difference between the two sites with a 95% confidence level and a 80% power.

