### **12.2. Description of Statistical Methods**

Comparison of response to the two different pacing sites will be made using appropriate statistical testing. We would expect the data to be normally distributed, in which case T-tests will be used.

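### Best-MPP AHR by site is open to drift between branches, because no spontaneous baseline is tied to the second branch and branch order is neither balanced nor recorded

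*Combined protocol and SAP*

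**What the plan says.** Section 5, item 4, sets out the sequence. First, "The baseline LV-dP/dTmax will be measured during ventricular spontaneous rhythm". Then the quadripolar lead "will be sequentially placed in the “peri-scar” CS branch and in the “remote myocardium” CS branch". Peri-scar is named first, but no sentence makes that order a rule. In each branch all four poles are tested for single-site pacing, and "3 different configurations will be used in turn for MPP". Each recording lasts at least thirty seconds.

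Section 9.2.4 repeats the sequence and adds two relevant sentences. One defines the response by site: "In each site the AHR to both conventional single-site and MPP LV pacing will be performed by measuring the percentage change", with spontaneous rhythm as the reference. The other reads "All measurements will be repeated at least twice in order to make sure they are reliable and reproducible".

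Section 12.3 lists spontaneous LV-dP/dTmax once, with no branch attached, but lists the pacing measurements by branch. It names two comparisons between sites: best-MPP AHR, and the gain of best MPP over single-site pacing. It expects both to be statistically significantly higher in the peri-scar region. Section 12.2 says "Comparison of response to the two different pacing sites will be made using appropriate statistical testing" and expects to use t-tests. It mentions neither pairing nor an order term.

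Nothing in the supplied text randomises, alternates or records which branch is tested first. The content of the Appendix A flow chart is not in the supplied text and could not be checked.

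**The concern.** AHR is a percentage change from a reference value. If the reference is taken before the first branch and contractility changes before the second, the second branch's AHR absorbs that change. With peri-scar tested first, a fall looks like a peri-scar advantage and a rise hides one.

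Time does pass between branches. Section 7.1.2 estimates 20 to 30 additional minutes on average for moving the lead and measuring AHR. The thirty-second rule secures a steady state within a recording, not between branches.

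Best-MPP AHR by site is one of two outcome measures under the primary objective, and section 12.1 uses the pilot "to confirm the validity of the study hypothesis to be further investigated in a bigger study". A bias shared by most patients would carry into that decision.

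**Working it through.** **The plan's own figure.** Section 12.1 suggests that 15 patients could give 80% power at 95% confidence. It gives a range of 0% to 40% but no SD, so the figure cannot be reproduced. Solved backwards (two-sided paired t, n = 15), it needs a standardised difference of 0.778. At the full 40 points that is an SD of differences of 40 / 0.778 ≈ 51 points. This supplies no usable SD for the drift question, so the SDs below are assumptions.

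**Inputs.** From the documents: n = 15, 4 + 3 = 7 settings per branch, at least 30 s per recording, at least two repeats. Assumed: size of drift, SD of paired differences, 5 minutes to move the lead, single-site gain 15%, MPP gain 18%.

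**Recording time before the lead moves.** One recording per setting: 7 × 30 s = 3.5 min. Two: 7 min. Three: 10.5 min. The repeat rule does not say whether repeats come before the move.

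**Size of the bias.** If LV-dP/dTmax changes by a fraction g before the second branch and the first baseline is kept, the error in that branch's AHR is g × (100 + AHR) points. For example, a 5% fall at an AHR of 20% gives 0.05 × 120 = 6.0 points. The table states drift directly in AHR points.

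**False-positive rate.** All 15 patients peri-scar first, no true site difference, two-sided 5% paired t-test with 14 df, noncentrality = drift × √15 / SD:

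| Common drift (points) | SD 8 | SD 10 | SD 12 | SD 20 |
|---|---|---|---|---|
| 1 | 7% | 7% | 6% | 5% |
| 3 | 27% | 19% | 15% | 8% |
| 5 | 62% | 44% | 32% | 15% |

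Drift that averages zero across patients leaves the rate at 5%.

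**Timing of repeats.** Assume 5 points in 12 min, or 0.42 points per minute. With one recording per setting before the move, the MPP blocks are 3.5 + 5 = 8.5 min apart, so the bias is 8.5 × 5/12 = 3.5 points. With two it is 12 min and 5.0 points.

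**Order split.** If k of 15 patients have peri-scar first, mean bias is drift × (2k − 15)/15. At 5 points, SD 10 and no order term:

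| Split | Mean bias (points) | False positives |
|---|---|---|
| 15/0 | 5.0 | 44% |
| 12/3 | 3.0 | 15% |
| 10/5 | 1.7 | 6% |
| 8/7 | 0.3 | 3% |

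With order recorded and modelled, the rate is 5% at each mixed split. Power for a true 8-point difference is then 63% at 12/3, 77% at 10/5 and 81.5% at 8/7, against 82.1% for a paired test without drift or order term.

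**Effect of an own-branch baseline.** Under the same 5-point linear drift with two recordings per setting, residual AHR bias is 0.12 points if settings run in the same order in both branches, and 1.6 in size if reversed in one.

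**The second outcome.** MPP over single-site pacing does not use the spontaneous baseline. Under the same drift its bias is 0.06 points with the same setting order in both branches, and about 2.6 in size if reversed in one.

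**The case against.** The strongest reply is that section 9.2.4 already requires repeats of all measurements, and the spontaneous recording is one of them. A reader might infer from section 12.3 that there is only one baseline. The text does not support that: on its face a repeat baseline is required, and what is open is when and where it is taken. The by-site definition of AHR can also be read as an own-branch reference. Both points stand, and they make this a gap in timing and placement. They do not close it, because every repeat could be made before the lead moves.

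Second, the stated objective is the added benefit of MPP over single-site pacing. The outcome that measures this directly is largely protected, and nothing suggests that setting order would be reversed between branches. This stands too, but section 12.3 attaches a significance hypothesis to best-MPP AHR as well.

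Third, section 12.1 says the pilot is more about exploring a relation than proving significance, and every drift value here is assumed. That limits the weight of the false-positive rates. The bias in the estimated site difference does not depend on whether a test is done.

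A reader might also infer that a shared order makes site and time inseparable in any analysis. That holds only without an own-branch baseline; with one, slow drift is largely removed even under a fixed order.

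**Conclusion.** The point holds as a cheap improvement that should be made. The plan does not tie a spontaneous recording to the second branch, and the supplied text does not balance or record branch order. Bias in best-MPP AHR needs three conditions together: one order in most patients, a first-branch baseline as denominator, and drift in a common direction. The bias is then about the size of the drift. At SD 10 and with all 15 patients in one order, false positives are 7%, 19% and 44% for 1, 3 and 5 points.

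The documents give no drift, no SD and no fixed order. They therefore do not support a claim that drift will occur, that the comparison is biased, or that both outcomes are equally exposed. Confidence is high on the omission and low on its size.

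**What to change.** **Main change**, in sections 5, 9.2.4 and 12.3:
- take one of the already required spontaneous recordings immediately before pacing in each branch, and use it as that branch's denominator;
- keep the order of single-site and MPP settings the same in both branches of a patient;
- record which branch was tested first.

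The cost is protocol wording, about one extra minute of recording per patient, and some noise, because two separate baselines no longer share one error. With an assumed 2% error per baseline and an AHR of 18%, SD 10 becomes √(100 + (1.18 × 2 × √2)²) = 10.5. If averaging two recordings cuts the error to 1.4%, it becomes 10.3.

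**Optional addition**, in sections 5, 9.2.4 and 12.2: where anatomy and operator judgement allow, alternate or randomise which branch is tested first (8/7), and specify a paired analysis with an order term. This also guards against common-direction drift that is not slow. It costs one degree of freedom (power 82.1% to 81.5% for 8 points at SD 10). Alternating order may also mean extra lead movement, and section 7.1.2 already warns that "there will be a slightly increased risk of damage to the CS venous system from extra manipulation of leads within it".

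Both changes together are not needed against slow drift. Under the 2% baseline error they take power from 82% to 77%. Final lead position stays with the operator, as the protocol already states.

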## 6. OBJECTIVES AND OUTCOME MEASURES

| Objectives   | Outcome Measures  | Timepoint(s) of evaluation of outcome measure |
|--|---|---|
| Primary

To assess whether the added benefit of multipoint pacing (MPP) over conventional single-site LV pacing is consistent in the peri-scar region compared to the remote myocardium | - Acute haemodynamic response to MPP (percentage increase of LV- dP/dTmax produced by MPP over spontaneous ventricular activation) in the peri-scar region and in the remote myocardium

- Percentage increase of LV dP/dT max produced by MPP over conventional single-site LV pacing in the peri-scar region and in the remote myocardium | CRT-D implant procedure                       |

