Although the MPP technology has a proven safety and efficacy profile comparable to the other CRT technology, evidence regarding the long term additional benefits of this pacing modality over conventional single site LV pacing is lacking. To this aim, a randomized multicentre study (MORE CRT MPP study) is currently underway to show the superiority of MPP over conventional single site LV pacing.

Some data are available about acute effects of MPP, i.e. the acute change in cardiac haemodynamics as MPP is activated.  $LV-dP/dT_{max}$ , consisting in the maximal rate of rise of LV pressure during cardiac contraction, is often measured to this aim. Basically a pressure manometer wire is temporarily placed into the LV during the CRT procedure and it continuously measures the left ventricular pressure. Studies investigating the Acute Haemodynamic Response (AHR) of MPP over conventional single site LV pacing with this or other techniques have documented small, variable and often not clinically significant improvements from MPP compared to single site LV pacing.

Study sub-analyses seem to suggest that MPP pacing could be particularly beneficial in specific subgroups of patients (12) and when stimulating particular areas of the LV, with up to 35-40% improvement in  $LV-dP/dt_{max}$  if compared to conventional single-site LV pacing in the same site (13). Studies using biophysical modelling suggest that MPP from a quadripolar lead may exert its benefit mainly in patients with ischaemic heart disease resulting in LV scar (14).

In order to optimize the response rate to CRT, it is extremely important to understand how MPP works, which subgroup of patients may benefit more from it and if a specific LV location should be chosen in order to have an added benefit from it. Of note, this pacing feature requires specific devices and higher energy, with increased battery drainage leading to more frequent battery changes and increased risk of infections so it is really important to understand when it is worth using it.

|  |                                    |                                      |
|--|------------------------------------|--------------------------------------|
| Subject: Research protocol                    | Short Title: SCAR MPP study | Chief Investigator: [name] |
| Version/Date: 1.1 /6 th April 2019 | IRAS Ref: 211326            | Ethics Ref: 16/SC/0662        |

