### 3.1 Research question and hypothesis

We plan to investigate if the added benefit of MultiPoint Pacing over conventional single-site LV pacing is related to the presence of scar in the left ventricle and the position of the pacing lead relative to it.

Our hypothesis is that MMP produces a better AHR compared to conventional single site LV pacing if there is scar in the left ventricle and when the lead is placed closed to the scar because this allows the recruitment of large areas of peri-scar viable tissue, characterized by slow conduction, with quicker electrical activation and more vigorous contraction (fig.2).

[figure not shown]

Fig.2. When positioned at sites of healthy myocardium, MPP gives no incremental benefit over conventional single site LV pacing because there are no areas of slow conduction and block (left panel). On the other hand, when the LV lead is positioned next to myocardial scar, where there are areas of slow ventricular conduction and block, MPP can improve the electrical activation by recruiting more tissue at the same time (right panel).

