### **12.3. Analysis of Outcome Measures**

The following measurements will be collected and analysed:

- LV-dP/dTmax during spontaneous ventricular rhythm;
- LV-dP/dTmax during single site LV pacing in 4 different pacing configurations (4 different poles used in turn), with the LV lead either in the peri-scar CS branch or in the remote myocardium CS branch. The pacing configuration producing the biggest LV-dP/dTmax over spontaneous ventricular rhythm will be considered the best pacing configuration in each CS branch and used for further comparisons and analyses;
- LV-dP/dTmax during single MPP LV pacing in 3 different configurations, with the LV lead either in the peri-scar CS branch or in the remote myocardium CS branch. The pacing configuration producing the biggest LV-dP/dTmax will be considered the best pacing configuration in each CS branch and used for further comparisons and analyses.

|  |                                    |                                      |
|--|------------------------------------|--------------------------------------|
| Subject: Research protocol                    | Short Title: SCAR MPP study | Chief Investigator: [name] |
| Version/Date: 1.1 /6 th April 2019 | IRAS Ref: 211326            | Ethics Ref: 16/SC/0662        |

The percentage change in LV-dP/dTmax produced by the best single site LV pacing configuration over spontaneous ventricular rhythm will represent the best Acute Haemodynamic Response (AHR) of single site LV pacing in each CS branch. The percentage change in LV-dP/dTmax produced by the best MPP LV pacing configuration over spontaneous ventricular rhythm will represent the best Acute Haemodynamic Response (AHR) of MPP LV pacing in each CS branch.

The following comparisons will be made as outcome measures:

- AHR produced by the best MPP configuration in the peri-scar region versus AHR produced by best MPP configuration in the remote myocardium;
- percentage increase of LV-dp/dTmax produced by the best MPP configuration over single site LV pacing in the peri-scar region versus percentage increase of LV-dp/dTmax produced by the best MPP configuration over the best conventional single-site LV pacing in the remote myocardium.

Our hypotheses are that:

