- the AHR produced by the best MPP configuration will be consistently and statistically significantly higher in the peri-scar region compared to the remote myocardium;
- the percentage increase of LV-dp/dTmax produced by the best MPP configuration over single-site LV pacing will be consistently and statistically significantly higher in the peri-scar region compared to the remote myocardium.

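### Two unranked primary outcome measures sit under one objective; only MPP over single-site pacing measures it, because MPP over spontaneous rhythm also carries the between-branch single-site difference

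*Combined protocol and SAP*

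**What the plan says.** The Synopsis and section 6 give a single objective, labelled primary, which asks if "the added benefit of multipoint pacing (MPP) over conventional single-site LV pacing is consistent in the peri-scar region compared to the remote myocardium". Section 3.1 puts the same question, asking "if the added benefit of MultiPoint Pacing over conventional single-site LV pacing is related to the presence of scar" and to lead position.

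Two outcome measures are listed under that objective, with no order between them:

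- First measure: acute haemodynamic response (AHR) to MPP, meaning the percentage increase in LV-dP/dTmax "produced by MPP over spontaneous ventricular activation) in the peri-scar region and in the remote myocardium".
- Second measure: the percentage increase of MPP over single-site LV pacing in the same two regions.

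Section 12.3 compares each between branches and attaches a significance hypothesis to each. The first reads: "the AHR produced by the best MPP configuration will be consistently and statistically significantly higher in the peri-scar region compared to the remote myocardium". For the second, the expectation is that the increase given "by the best MPP configuration over single-site LV pacing will be consistently and statistically significantly higher in the peri-scar region". Section 12.3 also derives a single-site quantity per branch, which "will represent the best Acute Haemodynamic Response (AHR) of single site LV pacing in each CS branch", but does not list a comparison of it between branches.

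**The concern.** The objective names single-site pacing as the comparator. The first measure does not use that comparator, yet it stands as a primary outcome with its own significance hypothesis. Both measures come from the same 15 patients and can disagree, and no section says which one answers the objective or what follows if they differ.

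Section 4 explains why this matters: MPP needs specific devices and more energy, and the authors want to know "if a specific LV location should be chosen in order to have an added benefit from it". If ordinary single-site pacing simply works better in one branch, the first measure will favour that branch even when MPP adds the same in both. If single-site pacing works less well near scar, the first measure can hide a real MPP gain there. Either result could steer the larger study that section 12.1 has in view.

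**Working it through.** **1. The plan's own figure.** Section 12.1 says 15 patients could be enough at 95% confidence and 80% power, citing "a variable AHR to MPP over single-site LV pacing with a percentage increase in LV-dP/dT between 0% and 40" per cent according to LV site. No SD is given, so the claim can be neither reproduced nor refuted. Section 12.2 says only that t-tests will be used. Assuming a paired two-sided test at 5%, n = 15 and 80% power, the exact noncentral t gives a detectable standardised difference of 0.778. A 40-point difference would then need an SD of the between-branch difference of at most 40 / 0.778 = 51.4 points. For this point, what matters is the scale: the 0 to 40% range is MPP over single-site pacing, which is the second measure. No sizing figure is given for the first.

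**2. The identity.** In each branch let S be the best single-site AHR over spontaneous rhythm and g the gain of best MPP over best single-site pacing, both as proportions. Sections 5 and 9.2.4 describe a spontaneous-rhythm baseline taken before the lead is placed in either branch, so both branches share it. Then

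MPP AHR = (1 + S)(1 + g) − 1.

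With p for peri-scar and r for remote:

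- First measure, difference: (S_p − S_r) + [g_p(1 + S_p) − g_r(1 + S_r)].
- Second measure, difference: g_p − g_r.

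The term S_p − S_r is the effect of lead position on ordinary single-site pacing. It is not part of the objective.

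**3. Two worked cases (assumed values).**

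| Case | S_p, S_r | g_p, g_r | MPP AHR peri-scar | MPP AHR remote | First-measure difference | Second-measure difference |
|---|---|---|---|---|---|---|
| A | 20%, 10% | 5%, 5% | 1.20 × 1.05 − 1 = 26.0% | 1.10 × 1.05 − 1 = 15.5% | 10.5 points | 0 |
| B | 15%, 20% | 5%, 0% | 1.15 × 1.05 − 1 = 20.75% | 1.20 × 1.00 − 1 = 20.0% | 0.75 points | 5 points |

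Check by the formula. A: 10 + (6.0 − 5.5) = 10.5. B: −5 + (5.75 − 0) = 0.75.

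**4. Range.** With an equal gain g in both branches, the first-measure difference is (S_p − S_r)(1 + g). At g = 5%, single-site differences of 0, 5, 10 and 15 points give 0, 5.25, 10.5 and 15.75 points, while the second measure stays at zero. Conversely, a 5% gain confined to the peri-scar branch is fully cancelled on the first measure by a single-site shortfall of 0.05 × (1 + S_p): 5.5, 5.75 or 6.0 points at S_p = 10%, 15% or 20%.

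**5. Which target do the documents intend?** Both framings appear.

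- MPP over single-site: the objective, section 3.1, and the 0 to 40% range in section 12.1.
- AHR to MPP: the study title and the opening sentence of section 12.1. Sections 9.2.4 and 12.3 define AHR against spontaneous rhythm, so these read most naturally as the first measure.

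The term itself shifts: the 12.1 sentence quoted in step 1 uses AHR for MPP over single-site pacing.

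**The case against.** The strongest reply has four parts.

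- **The matching measure is already there.** The second measure nearly repeats the objective's wording, and each hypothesis in 12.3 is stated in its own terms. This stands. The first measure validly tests its own hypothesis, and no section says it will be read as added benefit. The risk is inferred from its place under an added-benefit objective.
- **The first measure has its own support.** The title and the opening of 12.1 point to it, and total response by site bears on where a lead might go. This also stands. A reader might infer that the plan clearly intends only the second measure; the documents do not support that, because they frame the target both ways and do not choose.
- **This is a pilot.** Section 12.1 says the aim is to explore a relation more than to prove a significant difference. That lowers the weight. It does not remove the point, since 12.3 hypothesises significance twice and 12.1 wants the hypothesis confirmed for a bigger study.
- **Single-site AHR is already derived in each branch**, and 12.3 says the best configurations will go into further comparisons. True, but the between-branch comparison needed to interpret the first measure is not listed.

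A reader might also want a rate at which the trial would mislead. In a simulation with n = 15, paired two-sided 5% tests, mean gain 5% in both branches (SD 4 points each) and an SD of 10 points for the single-site difference, the first measure is significant in 5%, 33%, 87% and 99.6% of runs for single-site differences of 0, 5, 10 and 15 points. Those figures are essentially the power of a valid test against a difference that was put in. No section gives that difference, its direction or its SD, so they are not error rates of this trial.

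**Conclusion.** The point holds as a mismatch between one objective and two unranked measures. The first measure mixes the MPP gain with the between-branch single-site difference; the second isolates the gain. This follows from the plan's definitions and an exact identity, given a common spontaneous baseline, and needs no assumed figure. Its practical size is unknown: cases A and B show what is possible, not what is likely.

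The documents do not support saying that the first measure is invalid, that the trial cannot answer its objective, or that no significance level is given (12.1 states 95% confidence, though not whether tests are one- or two-sided). This is worth fixing, at the low end of that category.

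**What to change.** In the Synopsis, section 6 and section 12.3:

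1. Name the within-patient difference, peri-scar minus remote, in the percentage increase of best MPP over best single-site pacing as the primary outcome, and say that it answers the objective.
2. Keep MPP AHR over spontaneous rhythm as secondary, and report beside it the between-branch comparison of best single-site AHR, which 12.3 already derives.
3. Insert the word best before single-site pacing for the peri-scar branch in the second comparison of 12.3 and in the second hypothesis, to match sections 5 and 9.2.4.

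The cost is protocol wording and one added comparison of data already collected. The downside is one fewer primary claim.

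Keeping both measures as primary is possible but weaker. Requiring both to be significant would guard against case A but would block a true finding in case B. Splitting alpha to 0.025 each would raise the detectable standardised difference at n = 15 and 80% power from 0.778 to 0.876 (paired, two-sided) and would still not say which measure answers the objective.
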